### **1.3 Sample and Sample Size**

The sample for the trial consists of patients who have visited the PROUD trial PC clinics in the six participating health systems. Health systems were selected for the PROUD trial based on 1) leadership support for participating in the trial, 2) elements of clinic eligibility such as adequate size and having at least 3 PC providers willing to prescribe buprenorphine in each of the PC clinics, and 3) a demonstrated ability to obtain the secondary data necessary for the PROUD trial measures—specifically days of OUD treatment with buprenorphine and injectable naltrexone and days of acute care utilization. Smaller clinics were eligible if a group of clinics near each other included adequate numbers of patients (target ~10,000 unique patients with visits in a year), and were willing to participate as a single clinic for purposes of this trial, that is, if selected to implement the MA Model, a nurse care manager (NCM) would be shared between 2 intervention clinics.

PC patients 16-90 years old with at least 1 visit to the participating clinics from 3 years before to 2 years after randomization (the 5-year study period) will be included in the trial. The total sample of PC patients in the trial is anticipated to be over ~170,000 patients across the 12 clinics, since over 14,000 patients were seen, on average, in each clinic in 2016. The implementation objective is addressed in the total trial sample, while the secondary objective is evaluated in the subsample of trial patients who have EHR documentation of an OUD during the pre-randomization period.

## **2.0 GENERAL PROCEDURES AND DEFINITIONS**

### **2.1 Intent-to-treat (ITT) Analysis**

Unless otherwise specified, all analyses will follow an intent-to-treat principle whereby clinics (and patients therein) will be analyzed according to the treatment arm to which they were randomized regardless of the subsequent sequence of events.

### **2.2 Study Day 1**

The randomization date is defined as study day 0 and study day 1 is defined as the day after randomization.

### **2.3 Pre-randomization Period**

The pre-randomization period is defined as the period 3 years prior to randomization through study day 0 (randomization date), except at one health system that changed EHR systems where the pre-randomization period is limited to 2.8 years. For simplicity, throughout the SAP this pre-randomization period is referred to as 3 years. The pre-randomization period is used to define the Objective 2 primary sample. Including the randomization date in the pre-randomization period is appropriate because health systems were notified of their randomization status the day after the randomization date.

#### **2.3.1 Baseline Period**

Because all clinics have data 2 years prior to randomization through study day 0, many covariates for descriptive analyses and regression adjustment are defined over the 2 years prior to randomization through study day 0 (since all clinics have data from this period), referred to as “baseline” measures.

### **2.4 Follow-up or “Post-randomization” Period**

Unless otherwise specified, the follow-up period is defined as the period from study day 1 to 2 years after the randomization date (or 1.5 years for one health system that randomized 6 months late). For simplicity, throughout the SAP this follow-up (“post-randomization”) period is referred to as 2 years.

[figure not shown]
### **2.5 Study Period**

The study period is defined as up to 3 years pre-randomization (3 years at 5 health systems and 2.8 years at 1 health system) through up to 2 years following randomization (2 years at 5 health systems and 1.5 years at 1 health system). The full study period of up to 5 years—defined as the start of the pre-randomization period to the end of the follow-up period for each health system—is used to define the Objective 1 sample.

### **2.6 Data Collection Period**

For eligible patients (defined in Section “Study Population”), data are collected from 3 years prior to randomization through 2 years post randomization (Figure 1). Limited datasets are extracted from the EMR and insurance claims data during four interim time points (“Data Pulls” 1-4) during the post-randomization period for reports to the Data and Safety Monitoring Board and refinement of data specifications and measures (Table 1). Objective 1 and 2 analyses use data from Data Pull 5 collected after the end of follow-up.

**Figure 1: Data Collection Period**

**Table 1: Data Collection Timeline**

Data Pull Number	Cohort Eligibility*	Data Collection*	When data are transferred to Lead Node
			(Post randomization)
1	T-3 to T0	T-3 to T0	6 mo
2	T-3 to T0.5	T-3 to T0.5	12 mo
3	T-3 to T1	T-3 to T1	18 mo
4	T-3 to T1.5	T-3 to T1.5	24 mo
5	T-3 to T2	T-3 to T2	33 mo

\*T0 is randomization date.

### 3.0 STUDY POPULATION

Patients are eligible for inclusion in the trial if:

- 1) they had a PC visit at a PROUD trial PC clinic in the pre-randomization and/or follow-up period (defined above), and
- 2) age is 16 to 90 years at the time of a PC visit during the study period.

Eligible PC visits refer to outpatient clinic visits (in which the patient was age 16 to 90 on the day of the visit) to the departments of adolescent and pediatric medicine (including teen clinics), family practice, geriatric, general practice, or internal medicine that are provided by a physician, physician assistant, nurse practitioner, resident or fellow with one of these specialties.

#### 3.1 Assignment of Patients to Clinics

Patients will be assigned to clinics based on the number of eligible PC visits. In the rare case that a patient had PC visits to both PROUD Intervention clinics and UPC clinics, they will be assigned the clinic which they visited the most pre-randomization (if they visited during that period), and if they are tied, the clinic visited nearest to and preceding the time of randomization will be considered the patient's PC clinic. If a patient only had PC visits to a trial clinic post-randomization but not pre-randomization, and they visit both PROUD and UPC clinics, they will be assigned to the clinic they visited the most, and if tied they will be assigned to the clinic they visited last.

#### 3.2 Objective 1 Study Sample

The primary implementation (Objective 1) outcome, along with secondary implementation measures, will be analyzed among the full sample of eligible patients defined above.

#### 3.3 Objective 2 Primary Study Sample ("Pre-randomization Sample")

The primary effectiveness (Objective 2) outcome, along with secondary effectiveness measures, will be analyzed in the subset of patients from the full sample of eligible patients who had (1) an eligible PC visit at a PROUD trial PC clinic during the pre-randomization period, (2) a documented OUD diagnosis during the pre-randomization period, and (3) who were age  $\geq 16$  as of the start of the baseline period (two years pre-randomization). This latter criterion ensures that the patient has at least 2 years pre-randomization in which to have an eligible PC visit (in which they are  $\geq 16$  years of age). Clinic assignment for the Objective 2 primary sample will be the same as above. Because study sample is defined using pre-randomization data, this sample is also referred to as the Objective 2 pre-randomization sample.

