Mortality is an important outcome for OUDs. However, death data are obtained from the state and generally lag by 2 years. Further, while health insurance plans will often have data on the death of their enrollees, health delivery systems do not. Deaths will be documented in the EHR when known, but that process could be influenced by a NCM who reaches out to patients when they are lost to follow-up (biasing results). Therefore we will not use death from EHRs in main analyses, but a Health Systems Node (HSN) investigator with expertise in OUDs and mortality ([name]) has been invited to lead an ancillary study that will evaluate death in the sample for Objective 2 as well as conduct sensitivity analyses to determine whether deaths impacted main findings.¹²⁴⁻¹³⁰

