Health care utilization	Dates of visits related to study objectives e.g., PC, integrated behavioral health, mental health clinics, hospitalizations (admit/discharge dates), urgent care, ED, certified OUD treatment programs (where available), other substance use disorders treatment (inpatient and outpatient), hospice and palliative care. These data including all health care utilization data will be obtained for later cost analyses (planned ancillary study).
Diagnoses	All ICD-9 and ICD-10 diagnostic codes during the study period and dates, including but not limited to: OUDs; other substance use disorders (e.g., alcohol); mental health conditions (e.g., depression, anxiety), associated medical conditions (e.g., chronic pain, HIV, HCV, etc.), other relevant comorbidities and co-morbidity scores (e.g., Charlson and Elixhauser) for use characterizing the study samples, as covariates and as outcomes
Mortality	Death data will be obtained from all sites, although ~ 2 year lags in data result in under ascertainment.

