10.3.6 Incomplete Death Data

Most sites participating are not health insurance plans and do not have population based death data (i.e., from state vital status files). Relying on the EHR could bias the study towards greater ascertainment of OUD deaths in the PROUD intervention clinics due to NCM documentation. Mortality rates in patients with OUDs documented in EHRs are high (48.6 per 1000 person-years or a 10-fold increase over expected death rates (standardized mortality ratio of 10.3 (95% confidence interval [CI] 9.4–11.3)).³⁰ We address this below with sensitivity analyses and with an ancillary study to evaluate the intervention’s impact on death among patients with OUDs.

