## 8.0 OTHER CONSIDERATIONS

### 8.1 Missing Data

Given that the primary and secondary outcomes rely on the EHR data or insurance claims data, if there is no evidence of a particular event, such as provision of buprenorphine or a visit to the ED, we will assume that the event did not occur. These same assumptions apply to the only covariate in the primary analyses of the primary Objective 1 and Objective 2 measures (baseline value of the respective measure in the 2 years prior to randomization).

Our primary Objective 1 outcome uses medication orders to capture days of OUD medication treatment as orders were available for all health systems and dispensings are considered incomplete at 5 of the 6 health systems. However, because dispensing data and not medication orders are considered the gold standard, we will conduct sensitivity analyses in which we estimate the primary outcome at each health system using only medication dispensing data in the 3 health systems that have some dispensing data and pharmacies in both the usual care and intervention clinics (Section 5.2.4).

For Objective 2, given our visit-based sample we are not able to identify when a patient is no longer observable. To address this, we will conduct a sensitivity analysis for our Objective 2 outcome among the two health systems that are health insurance plans in which we use enrolled samples (Section 5.4.3). We will also conduct sensitivity analyses that restrict to patients with evidence of being active in the health system post-randomization (as described above in Section 5.4.2).

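### The Objective 2 primary sample does not require patients to be alive at randomization, so deaths before day 0 are analysed as full follow-up with no acute care; the rate ratio is unbiased in expectation, but reported rates and odds ratios are distorted

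*SAP*

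**What the plan says.** SAP 3.3 lists three conditions: an eligible primary care visit to a trial clinic before randomization, "a documented OUD diagnosis during the pre-randomization period, and (3) who were age" at least 16 "as of the start of the baseline period (two years pre-randomization"). The pre-randomization period is 3 years, except at one health system "where the pre-randomization period is limited to 2.8 years" (SAP 2.3). Neither document adds a condition on vital status, enrolment or activity at day 0.

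Three further rules decide how such a patient is analysed:

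- SAP 5.3 keeps everyone in the sample under intention to treat, including patients never seen after randomization.
- The offset in SAP 5.3 is the health system's potential follow-up, not the patient's time at risk.
- SAP 8.1 says that where there is no evidence of an event, "we will assume that the event did not occur".

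On deaths, Protocol Table 4 states "Death data will be obtained from all sites", while warning of under-ascertainment from a lag of about 2 years. Protocol 3.6.4.6 notes that nurse care manager (NCM) outreach could influence what is documented, and concludes: "Therefore we will not use death from EHRs in main analyses". Protocol 10.3.6 says: "Mortality rates in patients with OUDs documented in EHRs are high (48.6 per 1000 person-years". It promises sensitivity analyses, but Protocol 11.7.2 lists only incomplete ascertainment and crossover for this outcome, and no analysis in SAP 5.4 uses a date of death.

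**The concern.** Take a patient with a visit and an opioid use disorder (OUD) code 30 months before randomization who died 12 months before it. All three conditions are met. The patient enters the model with zero acute-care days, zero treatment days, a full offset, and any utilization before death in the last two years as the baseline covariate. The intervention could not reach this patient, and the zero carries no information about it.

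Four things are at stake. Reported utilization and treatment rates are too low in both arms. Odds ratios for binary outcomes are pulled towards 1, because adding equal shares of certain non-events does not cancel in an odds ratio as it does in a rate ratio. Some precision is lost. With 12 clinics, the dead may also fall unevenly between arms by chance.

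The protocol's reason for setting EHR deaths aside concerns deaths during follow-up, when the NCM may improve documentation in one arm. It does not by itself justify keeping patients whose death before day 0 is known from a source that the arm cannot touch.

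**Working it through.** **Inputs.** Clinic sizes from SAP 6.2.1: 9, 12, 63, 39, 58, 200, 100, 49, 27, 10, 388, 290, total 1,245. Mean acute care over 2 years from SAP 6.2.1: 4.0 × 2.04 = 8.16 days. Clinic random-effect SD τ = 0.23. Mortality m = 0.0486 per year (Protocol 10.3.6).

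**The plan's own figure.** SAP 6.2.2 states more than 80% power at a rate ratio of 0.65 with τ = 0.23, using the between-within correction (10 df). Re-simulating that model with 1,000 repetitions (one clinic per system randomized, Poisson counts, Wald t on 10 df) gives 84.3%, so the statement reproduces.

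**Share dead at day 0.** The documents give no count. Assumption: m applies from the date a patient qualifies until day 0. With qualifying dates spread evenly over L years, the share is 1 − (1 − e^(−mL))/(mL). If all qualify at the start of the window, it is 1 − e^(−mL).

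| Entry pattern | Share dead | Of 1,245 |
|---|---|---|
| Even over the last year | 2.4% | 30 |
| Even over 3 years | 7.0% | 87 |
| All at year −3 | 13.6% | 169 |

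With the 2.8-year window the last two shares are 6.5% and 12.7%. Protocol 3.1.1 prints the same 48.6 figure per 100 years and adds 18% dead over 7 years. Read as a constant rate, that 18% implies −ln(0.82)/7 = 0.028 per year, and even entry over 3 years then gives 4.1%, inside the range above.

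**Primary rate ratio and power.** With an equal share p dead in each arm, both means are multiplied by (1 − p), which cancels. Repeating the simulation at rate ratio 0.65 and τ = 0.23:

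| Share dead | Mean estimated rate ratio | Power |
|---|---|---|
| 0 | 0.65 | 84.3% |
| 7% | 0.65 | 82.8% |
| 13.6% | 0.65 | 81.8% |

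The losses are 1.5 and 2.5 points; the simulation standard error of each figure is √(0.843 × 0.157/1000) = 1.2 points.

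**Reported rates.** If the living average 8.16 days over 2 years, the reported mean is 8.16 × 0.93 = 7.59 at 7% dead and 8.16 × 0.864 = 7.05 at 13.6%. Per year that is 4.08 falling to 3.79 or 3.53.

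**Odds ratio for any acute care.** Illustration with an assumed 60% in usual care and 50% in PROUD: the true odds ratio is (0.5/0.5)/(0.6/0.4) = 0.667. At p = 7% the proportions become 0.558 and 0.465, and the odds ratio is (0.465/0.535)/(0.558/0.442) = 0.688. At 2.4% it is 0.674 and at 13.6% it is 0.707. The log odds ratio shrinks by 3%, 8% and 14% at 2.4%, 7% and 13.6%.

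**Chance imbalance.** If 10% were dead in PROUD and 5% in usual care, the rate ratio would be 0.90/0.95 = 0.95 with no true effect.

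**The case against.** The strongest objection is to the obvious remedy. A death before day 0 cannot be caused by the arm, but its recording can be. A patient who died in month −6 and is sought by the NCM in month +8 may get a recorded death in a PROUD clinic and none in usual care. If 7% were dead in both arms and all were removed in PROUD but only half in usual care, an unbiased rate ratio would be multiplied by 0.965/0.93 = 1.04. SAP 3.4 explains that this sample was chosen to avoid that kind of identification bias. The objection stands: a filter on any death date present in Data Pull 5 would be unsafe. It does not apply to records made before the NCM is active, or to state and health-plan files.

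The plan also has partial cover. SAP 5.4.3 considers an analysis of patients enrolled at randomization with enrolled time as offset, but only in two systems and depending on subsample size. SAP 5.4.6 requires a visit in the last year, which under even entry cuts the share dead from 7% to about 2.4%, but it tightens the diagnosis rule at the same time. Protocol 3.6.4.6 assigns an ancillary study to test whether deaths affected the main findings; Protocol 4.4 starts that study at least 2 years after the intervention ends. SAP 5.4.2 is not a substitute, because it selects on contact after randomization, which the intervention may change.

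Two further limits stand. Most sites lack population-based death data (Protocol 10.3.6), so many such deaths cannot be found. Patients who moved away before day 0 produce the same unobservable zeros and would remain.

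**Conclusion.** The gap is real and follows from SAP 3.3, 5.3 and 8.1 read together. Its effect on the main Objective 2 test is small: no bias in expectation, and a power loss of about 1.5 to 2.5 points even if every such death could be removed. It matters more for reported days per year and treatment rates, understated by about 7% (range 2% to 14%), and for odds ratios, attenuated to a similar degree. These sizes rest on applying 48.6 per 1000 person-years from qualification to day 0. The odds-ratio example also rests on an assumed 60% versus 50%. The achievable correction is a fraction of these figures.

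A reader might infer more, in three ways that the documents do not support:

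- **That the primary rate ratio is biased.** These deaths precede randomization, so their shares are balanced in expectation and cancel.
- **That small clinics make the problem serious.** In the clinic with 9 patients one death lowers the mean by 11%. Even with clinics weighted equally, that shifts the arm's log rate by ln(8/9)/6 = −0.02, well inside the variation implied by τ = 0.23.
- **That deaths after randomization should now enter the main analysis.** The protocol's reason against that is unaffected.

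**What to change.** Add to SAP 3.3, and to SAP 3.4 for patients entering through the pre-randomization period, an exclusion for a date of death on or before study day 0. Limit the sources to those the arm cannot influence:

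- Deaths already recorded in the baseline extraction (Data Pull 1). Protocol Table 10 places it 0–3 months after randomization, before NCM training at about 4 months (Protocol 9.3.3). SAP Table 1 gives only a transfer date of 6 months, so confirm the extraction date at each site.
- State vital-records or health-plan death files where a site has them. These may come from a later pull; Data Pull 5 at 33 months is past the usual 2-year lag for deaths before day 0.

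Do not use EHR death entries made later in follow-up. Report the number removed by arm and clinic in the cohort figure, and show the primary result with and without the exclusion. Keep the rule against using deaths after randomization in main analyses.

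The cost is a short addition to the SAP, one filter on data already collected and one extra result line. The downside is that death capture is incomplete and differs between health systems, so some deaths before randomization will stay in the sample.

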#### 3.4 Objective 2 Secondary Study Sample

The Objective 2 primary sample as defined in the preceding section, which restricts analyses to patients seen in PROUD trial clinics with documented OUD pre-randomization, was selected for primary analyses to avoid the potential for *identification bias* (type of selection bias that can occur when the analytic sample is defined using post-randomization data). However, an important limitation of analyses within the Objective 2 primary sample is that they miss any impact of the PROUD intervention among patients with a new OUD diagnosis post-randomization, including patients who initiate treatment in PROUD intervention clinics who are diagnosed with OUDs after randomization, and patients who are newly attracted to the clinic specifically because of the PROUD intervention. To address this limitation, secondary analyses are conducted in a broader sample that includes patients new to the PROUD trial clinics or with newly recognized OUDs post-randomization (see Figure Shell 1, Objective 2 paper, Section 10.2).

Specifically, the effectiveness (Objective 2) secondary study sample is defined as the subset of patients from the main trial sample who had a documented OUD diagnosis during either the pre-

randomization or follow-up periods and who were age  $\geq 16$  as of the start of the baseline period. Clinic assignment for the Objective 2 secondary sample will be the same as above.

#### **3.4.1 Objective 2 “Post-randomization Sample”**

We note that the Objective 2 secondary study sample is a broader sample that includes the Objective 2 primary “pre-randomization” study sample as a subset (Figure Shell 1, Objective 2 paper, Section 10.2). We refer to patients who are included in the secondary study sample but who are not included in the primary pre-randomization sample as having “newly recognized OUD in trial clinics post-randomization,” and we refer to this sample of patients as the “post-randomization” Objective 2 sample. This post-randomization sample consists of patients who were new to the trial clinics or with newly documented OUD post-randomization (see Supplemental Figure Shell 1, Objective 2 paper, Section 10.2, which illustrates the different ways patients can enter the post-randomization sample).

## 4.0 OUTCOME MEASURES

### 4.1 Definition of Primary Implementation Outcome Measure

The primary outcome (clinic-level measure) is the number of patient days of OUD medication treatment documented in the EHR in each clinic post-randomization. To account for varying clinic sizes, the clinic-level outcome is divided by the number of patients seen in the clinic post-randomization and then multiplied by an appropriate scaling factor in order to report the results (e.g., multiplying by 10,000 to calculate the number of patient days of OUD treatment per 10,000 patients), and reported as patient-years of treatment provided by a clinic (calculated by simply dividing days of OUD treatment by 365).

“OUD medication treatment” includes medications for OUD that can be prescribed in PC and documented in EHRs—buprenorphine formulations indicated for OUD (oral, implants, sustained release injection with or without an OUD diagnosis) or injectable extended release (XR) naltrexone with a diagnosis of OUD. An OUD diagnosis is required for injectable XR naltrexone because it is often used for alcohol use disorders (AUD). We do not require an OUD diagnosis for buprenorphine because there are buprenorphine formulations specific for OUD and PROUD Phase 1 analyses revealed OUD diagnoses are often missing, consistent with the literature. Further, an OUD diagnosis is likely to be documented by PROUD clinic providers based on the PROUD NCM manual, so that requiring an OUD diagnosis could bias findings toward favoring the intervention clinics.

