## 5.0 ANALYSES OF OUTCOME MEASURES

### 5.1 Primary Analytic Method for Primary Implementation Outcome Measure

Since randomization and the intervention occur at the clinic-level, the unit of analysis will be clinic and not patient for the primary outcome. The mixed effects model evaluating the effect of the PROUD intervention is:

$$y_{ij} = \alpha + \beta * trt_{ij} + \gamma * z_{ij} + \theta_j + \epsilon_{ij} \quad (1)$$

where

- 1)  $y_{ij}$  is the observed value of the primary outcome measure for clinic  $i$  at health care system (HCS)  $j$
- 2)  $trt_{ij}$  is the treatment indicator (PROUD intervention) for clinic  $i$  at HCS  $j$
- 3)  $z_{ij}$  is the observed value of the primary outcome measure for the two years prior to randomization (hereafter baseline) for clinic  $i$  at HCS  $j$
- 4)  $\theta_j$  is the random effect for HCS  $j$  and is distributed  $N(0, \sigma_{\theta}^2)$
- 5)  $\epsilon_{ij}$  is the error term for clinic  $i$  at HCS  $j$  and is distributed  $N(0, \sigma_{\epsilon}^2)$

Our primary hypothesis is that there will be a significant increase in the number of patient days of medication treatment for OUDs during the follow-up period in clinics randomized to the PROUD intervention as compared to clinics randomized to UPC. To evaluate this hypothesis, analyses test whether  $\beta$  (PROUD intervention effect) significantly exceeds zero using a one-sided hypothesis test at the 0.05 level. This is appropriate because our primary aim is to test superiority of implementation of the MA model relative to Usual PC in order to inform health systems' decisions as to whether to implement this model of OUD care.

Example SAS code for the analysis is as follows:

```
proc mixed data = primout;
  class arm;
  model scaletotdays = arm basevalue / solution;
  random intercept / subject = site;
  estimate "Treatment Effect" arm 1 -1;
run;
```

where "arm" is the treatment assignment ( $trt_{ij}$ ), "scaletotdays" is the value of the primary outcome measure ( $y_{ij}$ ), "basevalue" is the value of the primary outcome measure for the two years prior to randomization ( $z_{ij}$ ) and "site" indexes the different HCSs ( $j$ ).

This model allows for clinics to be correlated within a HCS, in addition to allowing for an association of the scaled days of OUD treatment prior to randomization with the post-randomization outcome.

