## **5.2.2 Modified Analyses Accounting for Success of Implementation**

Our Objective 1 analysis considers days of OUD treatment over the entire follow-up period since randomization. However, it took time for HCSs to hire the NCM, and for the NCM to start seeing patients once hired, and it is possible some may have never succeeded in implementing the model. We therefore plan to conduct two modified analyses, which will apply the same statistical model as the primary analysis but will either modify the definition of the follow-up period over which the Objective 1 outcome measure will be calculated or will restrict which HCSs are included.

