### **5.2.2.a. Analysis During the Period in Which the NCM was Seeing Patients**

First, we will modify the time period over which the main outcome is calculated to only include periods after which the NCM has engaged a patient in OUD treatment in the intervention clinic. For example, if the intervention clinic of a HCS hired the NCM 16 weeks after randomization and s/he was trained 8 weeks later and s/he engaged the first patient 1 week after training, for that HCS we would define the time period from 23 weeks post randomization until the end of the follow-up period, for both the clinic randomized to the PROUD intervention and the clinic randomized to UPC.

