Because one of the HCSs was randomized at a later date than the others, not all HCSs have the same amount of follow-up time. To account for this difference, we will include in the model an offset term for the number of days of potential follow-up time (e.g., 2 years for 5 of the HCSs and 1.5 years for the 6th HCS); in the above model,  $\log(\text{days}_j)$  denotes the offset term where  $\text{days}_j$  denotes the days of follow up in HCS  $j$ .

We will evaluate our primary Objective 2 hypothesis by testing the null hypothesis  $H_0: \beta = 0$  versus the two-sided alternative hypothesis that  $\beta$  is non-zero with a type 1 error rate of 0.05. In cluster-randomized trials with a small number of clusters, a small-sample correction is often necessary to obtain correct type 1 error rates. Although small-sample degree of freedom (DF) correction methods have been evaluated for continuous and binary outcomes under generalized linear mixed-effect models (GLMMs), there has not been prior guidance of which approach to use in our setting with a count outcome and covariate adjustment. Given this lack of knowledge, members of the PROUD statistical team are conducting simulations to evaluate alternate small-sample DF methods in this setting. Our results so far suggest that the optimal choice of testing procedure varies depending on the data-generating scenario in terms of the intraclass correlation

coefficient (ICC), number of clusters, and sample size within a cluster; however, using the likelihood ratio test with the Between-Within (BW) DF correction method (also referred to as “inner-outer” approach) appears to perform generally well in the scenario that aligned most closely with PROUD Phase 1 data used in the power simulation (see Appendix C).

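### Objective 1 totals treatment days without allowing for length of follow-up: a mild dilution and a mislabelled 2-year estimand in the primary analysis, and a more serious comparability problem in SAP 5.2.2.a

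*SAP*

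**What the plan says.** SAP 4.1 defines the primary outcome as total treatment days in a clinic after randomization, where "the clinic-level outcome is divided by the number of patients seen in the clinic post-randomization" and then scaled, for example to 10,000 patients. Reporting in patient-years is "calculated by simply dividing days of OUD treatment by 365", which changes the unit and does not divide by length of follow-up.

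SAP 2.4 sets follow-up at two years, "or 1.5 years for one health system that randomized 6 months late", and calls it two years throughout for simplicity. In SAP 5.1 the baseline covariate "is the observed value of the primary outcome measure for the two years prior to randomization", for every clinic. The SAS statement is "model scaletotdays = arm basevalue / solution" with a random HCS intercept. There is no offset, weight or duration term.

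SAP 5.2.2 describes modified analyses that "will apply the same statistical model as the primary analysis". In 5.2.2.a the clock starts, for both clinics of an HCS, once the nurse care manager (NCM) has engaged a patient. In the worked example, "we would define the time period from 23 weeks post randomization until the end of the follow-up period".

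Objective 2 is treated differently. On the late HCS, SAP 5.3 says: "To account for this difference, we will include in the model an offset term". SAP 5.4.5 changes that offset when follow-up is restricted to the NCM-active period. I found no counterpart for Objective 1.

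**The concern.** A total over 1.5 years and a total over 2 years are different quantities. The random intercept absorbs a level shift shared by both clinics of an HCS. It cannot restore an arm contrast that had less time to build up. A single baseline slope also cannot fit both 2-year-on-2-year and 1.5-year-on-2-year pairs exactly. The estimate labelled as a two-year effect is therefore a mixture.

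In 5.2.2.a potentially all six windows differ. That analysis is meant to show the effect while the NCM was working, and Supplementary Table 5 sets it beside the primary result in the same units. Without division by window length, a difference between the two rows may reflect only the amount of time counted.

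**Working it through.** **1. Reproducing the plan's power.** Inputs from SAP 6.1.2 and Table 4: intercept 0.05, slope 0.94, error SD 0.10, HCS SD 0. The stationary mean is 0.05/(1 - 0.94) = 0.833 treated days per patient, and a k-fold effect adds (k - 1) × 0.833 in intervention clinics. The simulated baseline is 2016-17 and the outcome 2018-19. The fit has arm, baseline and a random HCS intercept, with a one-sided 0.05 t-test on 4 df. Baseline-adjusted power, SAP Table 5 against recomputed: 49% and 49.1% at 1.18-fold, 84% and 84.0% at 1.30-fold, 98% and 97.5% at 1.42-fold. The plan's figures are reproduced.

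**2. How much a 1.5-year total shrinks at a constant treatment rate.** Days fall to 1.5/2 = 0.75, but fewer unique patients are seen. Protocol Table 2 gives the 3-year number seen and the two 2016 clinic counts. Assume that the number seen grows as time to the power b, with b = ln(ratio)/ln 3.
- Smallest growth (MC): 27,031/(9,776 + 9,138) = 1.429, b = 0.325, patients at 1.5 versus 2 years 0.75^0.325 = 0.911, outcome ratio f = 0.75/0.911, about 0.82.
- Largest growth (HH): 60,463/(11,390 + 17,652) = 2.082, b = 0.667, patients 0.825, f = 0.75/0.825 = 0.91.

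With an unchanged patient count, f = 0.75.

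**3. Dilution of the pooled effect**, assuming equal contrasts in all six HCSs: (1 - f)/6.
- f = 0.91: 1.5%
- f = 0.82: 3.0%
- f = 0.75: 4.2%

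If days instead ramp linearly after the 6-month start-up in Protocol 7.1.1, with no plateau (assumption), the 1.5-year total is (12/18)² = 0.444 of the 2-year total. With a patient ratio of 0.89, inside the 0.825-0.911 range, f = 0.444/0.89 = 0.50 and the dilution is 0.50/6 = 8.3%.

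**4. Effect on the primary test**, multiplying both clinics of one HCS by f:

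| f | Type I error | Power at 1.30-fold | Mean effect at 1.30-fold (UPC mean = 1) |
|---|---|---|---|
| 1 | 5.9% | 83% | 0.300 |
| 0.91 | 5.6% | 83% | 0.296 |
| 0.82 | 5.0% | 81% | 0.291 |
| 0.75 | 5.0% | 78% | 0.286 |

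The type I error differences are of the order of simulation noise; the first null run, also at f = 1, gave 4.6%. Power at 5-fold is 100% in every row.

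**5. Section 5.2.2.a.** The documents give no NCM dates, so windows of 53 to 90 weeks are assumed (mean 70% of two years). If the contrast accrues evenly from day 1, the 1.30-fold effect falls from 0.300 to 0.211 and power to 72%. If instead there is no contrast before the NCM's first patient, dropping those weeks removes none of it: the total is about the primary contrast again, apart from any change in the patient count. Neither figure measures the effect per unit of active time.

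**6. The worked example.** Hiring at 16 weeks, training 8 weeks later and a first patient 1 week after that gives 16 + 8 + 1 = 25 weeks, not 23. On a 104-week follow-up, 25/104 = 24% of the window is excluded.

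**7. What annualising does to the short HCS**, relative to a 2-year HCS: divide f by 0.75.
- Constant rate: 0.82/0.75 = 1.10 to 0.91/0.75 = 1.21, an overshoot of 10-21%. At a patient ratio of 0.89, 0.84 becomes 1.12.
- Ramp: 0.50/0.75 = 0.67, still a third short.

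**The case against.** The strongest reply is that the primary analysis has no validity problem, and that stands. Randomization is within HCS and both clinics of an HCS share one window, so the arms are treated alike. A reader might infer that the test is biased or that the trial loses meaningful power. The documents do not support that: type I error holds, and the design target in SAP 6.1 is a 5-fold increase. Nor is the two-year baseline an error in itself. It is a covariate with a free slope and need not share the outcome's time unit. The 1.5-year exception is also openly disclosed.

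The larger dilution figure is fragile. It needs zero effect before month 6 and unlimited linear growth afterwards, whereas Protocol 10.2.2 gives the NCM a finite capacity of about 100-125 patients. Equal contrasts across HCSs are also assumed, although clinics in SAP Table 3 range from 0.001 to 1.361 treated days per patient in 2015-16.

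For 5.2.2.a, it is fair to say that the excluded weeks should hold little contrast, so losing 24% of a window does not mean losing 24% of the effect. The Table 7 shell would also list each clinic's window in days. But listing is not scaling, and step 5 shows that the unscaled total is hard to interpret under either assumption.

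A reader might also infer that dividing by years cures everything. Step 7 shows that it does not. Many outcomes under 5.6 count unique patients or prescribers, for which a per-year figure is not a meaningful rate. SAP Table 2 also marks the two-year total as the registered primary measure, so redefining it is more than a cosmetic change.

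**Conclusion.** The omission is real, and the Objective 2 offsets show that the authors had recognised the issue. In the primary analysis it is a matter of estimand and labelling: roughly 2-4% dilution at a constant treatment rate, more under a ramp (about 8% in the linear case). These sizes rest on the assumed growth in patient numbers, the shape of uptake and equal contrasts across systems. There is no type I error problem and no loss of power at 5-fold; power at 1.30-fold falls from 83-84% to between 78% and 83%.

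In 5.2.2.a the problem is more serious. The estimate depends on how much time each HCS contributes and is not comparable with the primary result beside which it is tabled. Its actual size cannot be given without the NCM start dates.

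**What to change.** 1. **SAP 5.2.2.a:** compute both treatment days and the patient denominator over the actual window, and express the outcome per year of that window, with the baseline also per year.
2. **SAP 4.1, 5.1 and the subgroup versions in 5.7.1:** report patient-days per 10,000 patients per year of follow-up, baseline likewise. Alternatively, keep the registered total as primary and add the per-year version as a sensitivity analysis. In either case add a sensitivity analysis on a common 18-month post-randomization window for all six HCSs.
3. **SAP 5.6:** do not annualise counts of unique patients or prescribers; use the common 18-month window for those.
4. **Worked example in 5.2.2.a:** reconcile to 25 weeks.

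The cost is a little programming on data already held. In the primary analysis the five two-year systems change only in scale. The downsides are that the per-year measure overshoots somewhat at a constant treatment rate, and that its display scale differs from the registered two-year measure unless multiplied by 2. The 18-month analysis discards the last six months in five systems, which is why it is proposed only as a sensitivity analysis for the primary outcome.
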